So the aim of this study was to evaluate the effect of three types of rapid maxillary expanders (conventional, Hybrid and MSE) using cone beam computed tomography (CBCT)

Aim of study

The aim of this study was to compare the effect of three types of rapid maxillary expanders (conventional, Hybrid and MSE) using cone beam computed tomography (CBCT)

The secondary outcomes

- a- Evaluation of periodontal condition of maxillary first permanent molars, both clinically and radiographically using CBCT
- b- Evaluation of Airway.

Material and Methods

Study design:

Prospective randomized controlled trial

Study setting and population:

This study will be conducted on patients seeking orthodontic treatment in the outpatient clinic, Orthodontic department, Faculty of Dental Medicine, Al-Azhar University, Cairo, Boys branch.

Eligibility criteria of population:

The patients will be selected according to the following inclusions criteria:

- 1- Patients suffering maxillary collapse with a skeletal background
- 2- Patients with unilateral or bilateral posterior crossbite.
- 3- Patients with reduced or average anterior face height.
- 4- Patients with no periodontal disease.
- 5- Patients with good oral hygiene and general health.
- 6- No systemic diseases that may affect bone quality or interfere with orthodontic treatment.
- 7- Patients with erupted maxillary permanent first molars and premolars.
- 8- Patients with no previous orthodontic treatment.

Sample size:

Sample size calculation using G power software was based on the observed effect sizes derived from previous article. ⁽²⁰⁾

The calculation indicated that for a study with a power of 0.95 and an alpha of 0.05, a total of at least 45 patients (15 patients in each group) .

Group allocation:

The patients will be classified and randomly allocated into three equal groups, using online generated randomization plan (Graph Pad) found at the website

<http://www.graphpad.com/quickcalcs/index.cfm>:

- Group (1): The conventional hyrax.
- Group (2): The Hybrid hyrax.
- Group (3): The MSE expander.

Interventions:

The current study was conducted on a total sample of forty five young adult orthodontic patients presented with transverse maxillary deficiency with an age ranged from 11-16 years.

- All patients in this study will undergo a special protocol for oral hygiene measures for one month to standardize as possible the oral hygiene measure before expansion.
- The following diagnostic records will be taken for each patient before and after the completion of expansion treatment:
- Orthodontic study casts.
- Standardized extra-oral and intra-oral photographs.
- Panoramic and Upper occlusal radiographs.
- Other radiographic evaluations that serve the purpose of the study according to the situation.

- Radiographic analysis will be performed for each patient to evaluate the effect of the rapid maxillary expansion on the nasal airway.

Ethical consideration:

The objectives of the study will be discussed to the patients and parents and informed consent will be signed before treatment (form is attached).

Data management and analysis:

- The collected data will be statistically analyzed using SPSS.

The Institutional Ethical Committee: approval number **775/220**

References

4. Haas AJ. Rapid expansion of the maxillary dental arch and nasal cavity by opening the midpalatal suture. *Angle Orthod.* 1961;31(2):73-90.

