- **Molar inclination:** There was no significant difference between groups, regarding pre and post values ( $p= 0.353$ ;  $p=0.734$  respectively in right side and  $p=0.312$ ;  $p=0.892$  in left side). The mean value of amount of change (difference) recorded in MSE was significantly higher than that recorded in Butterfly hydrax and Hybrid hyrax, ( $p= .000$  in right side and  $p=0.003$  in left side). (Table 2, Fig 6, 15)
- **Premolar inclination:** There was no significant difference between groups, regarding pre values ( $p= 0.191$  in right side and  $p=0.355$  in left side). Post treatment, the mean value recorded in Butterfly hyrax was significantly higher than the other groups ( $p=0.003$  in right side and  $p=0.000$  in left side). The mean value of amount of change (difference) recorded in MSE was significantly higher than that recorded in Butterfly hydrax and Hybrid hyrax, ( $p= .000$  in right side and  $p=0.000$  in left side). (Table 2, Fig 7, 15)
- **Arch depth:** There was no significant difference between groups, regarding pre values ( $p= 0.064$ ). Post treatment, the mean value recorded in MSE was significantly lower than the other groups ( $p=0.007$ ). The mean value of amount of change (decrease) recorded in MSE was significantly greater than that recorded in Butterfly hydrax and Hybrid hyrax, ( $p= .000$ ), (Table 3, Fig 8, 16)

- **Incisor inclination:** There was no significant difference between groups, regarding pre and post values ( $p= 0.243$  and  $p=0.922$  respectively). The mean value of amount of change (decrease) recorded in MSE was significantly greater than that recorded in Butterfly hydrax and Hybrid hyrax, ( $p= .001$ ), (Table 3, Fig 9, 18)
- **Anterior suture opening:** There was no significant difference between groups, regarding pre values ( $p= 0.290$ ). The mean value recorded in MSE post treatment was significantly higher than that recorded in Butterfly hydrax and Hybrid hyrax, ( $p= .000$ ). The mean value of amount of change (increase) recorded in MSE was significantly higher than that recorded in Butterfly hydrax and Hybrid hyrax, ( $p= .001$ ), (Table 3, Fig 10, 18)

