	Hybrid hyrax	76.99	6.07	78.65	5.55	1.65	2.50	1.10	.000*
	MSE	75.14	5.83	76.16	5.95	1.02	.47	1.10	.000*
	P value bet. groups	.455ns		.283ns		.410ns			

Significance level p≤0.05, \*significant, ns=non-significant

Post hoc test: Within the same comparison, means sharing the same superscript letter are not significantly different

Table (2) Descriptive statistics and comparison between (ANOVA test) and within group (i.e. between pre and post value) (paired t test) regarding nasal floor, hard palate maxillary width molar and premolar; molar and premolar inclination right and left

GROUP	Pre		Post		Amount of change (post-pre)			P Within group	
	Mean	Std. Dev	Mean	Std. Dev	Mean	Std. Dev	Median		
Nasal floor 1 st .molar	Butterfly hyrax	65.13	5.07	67.33	1.67	2.20 b	1.49	1.80	.003*
	Hybrid hyrax	63.48	3.13	66.08	2.80	2.60 b	1.04	2.40	.000*
	MSE	62.00	3.36	66.38	3.07	4.38 a	.85	4.45	.000*
	P value bet. groups	.058ns		.397ns		.000*			
Nasal floor 1 st .premolar	Butterfly hyrax	34.57	1.55	37.04 c	1.17	2.47 c	1.02	2.40	.001*
	Hybrid hyrax	35.21	2.09	38.63 b	1.77	3.43 b	.74	3.50	.000*
	MSE	34.86	2.40	39.73 a	2.27	4.87 a	.62	5.00	.000*
		.701ns		.001*		.000*			
Hard palate Maxillary width 6	Butterfly hyrax	60.43	2.49	63.59 ab	2.15	3.17 b	1.54	3.10	.000*
	Hybrid hyrax	58.67	2.99	62.04 b	2.68	3.37 b	.96	3.40	.000*
	MSE	58.39	2.44	64.31 a	1.80	5.91 a	.92	6.10	.000*
	P value bet. groups	.083ns		.023*		.000*			
Hard palate Maxillary width 4	Butterfly hyrax	33.66	1.85	38.17 b	1.76	4.51 b	1.28	4.50	.001*
	Hybrid hyrax	34.22	1.79	39.31 ab	1.39	5.09 b	1.16	4.90	.001*
	MSE	33.99	1.58	40.34 a	1.56	6.35 a	1.25	6.10	.003*
	P value bet. groups	.677ns		.002*		.001*			
Right.1 st molar inclination	Butterfly hyrax	18.58	4.41	24.24	5.32	5.66 a	1.52	5.80	.000*
	Hybrid hyrax	18.43	5.33	23.27	5.20	4.85 a	2.10	6.00	.000*
	MSE	20.74	5.06	22.82	4.77	2.08 b	1.30	1.70	.000*
	P value bet. groups	.353ns		.734ns		.000*			
Left.1 st molar inclination	Butterfly hyrax	18.45	4.34	23.67	6.07	5.21 a	2.74	6.30	.000*
	Hybrid hyrax	19.09	3.08	23.71	3.68	4.62 a	1.62	4.90	.000*
	MSE	20.49	3.78	23.01	3.53	2.52 b	1.31	2.35	.000*
	P value bet. groups	.312ns		.892ns		.003*			

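### Periodontal condition is assessed at the first molars only, which can understate the conventional arm's relative periodontal harm, chiefly against Hybrid, if harm follows tipping

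*Protocol*

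**What the plan says.** The protocol lists two secondary outcomes. The first is "Evaluation of periodontal condition of maxillary first permanent molars, both clinically and radiographically using CBCT"; the second is the airway. No periodontal measure is planned at any other tooth. The premolars are available in every patient, because one inclusion criterion reads "Patients with erupted maxillary permanent first molars and premolars".

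The SAP, which already contains results, reports premolar distance, rotation and inclination, and nasal floor and palatal width at premolar level. It gives no periodontal analysis or result for any tooth.

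On tipping, the right first-molar rows of outcome Table 2 (the Table 2 in the Outcomes part, not the crossbite table with the same number) read "Butterfly hyrax 18.58 4.41 24.24 5.32 5.66 a 1.52 5.80 .000" for the conventional arm and "Hybrid hyrax 18.43 5.33 23.27 5.20 4.85 a 2.10 6.00 .000" for Hybrid. The mean changes, 5.66 and 4.85, carry the same letter. For premolar inclination the narrative says: "Post treatment, the mean value recorded in Butterfly hyrax was significantly higher than the other groups".

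**The concern.** The same tooth is read in all three arms, which looks even-handed. A single index tooth serves a between-arm comparison well if it represents each appliance's dental effect about equally. Here it may not. By the trial's own measurements, the conventional expander tips the first premolar nearly as far as the first molar, while the other two appliances tip it less than half as far.

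At stake is the periodontal contrast between conventional and Hybrid. The plan reads it at the tooth where their tipping is similar and not at the tooth where their tipping differs clearly. A finding of little periodontal difference at the molars could then be taken as a statement about the appliances as a whole.

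**Working it through.** **Inputs.** Mean change (post minus pre) in inclination and its SD, from SAP outcome Table 2. Group sizes 15, 15 and 16 come from the SAP demographic tables. Two assumptions: the arm the SAP calls Butterfly is the protocol's conventional hyrax (the SAP heading naming Hybrid and conventional groups supports this), and inclination is in degrees (the table prints no unit).

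**Step 1: reproduce the printed changes** as post mean minus pre mean.

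| Tooth | Conventional | Hybrid | MSE |
|---|---|---|---|
| Right molar | 24.24 − 18.58 = 5.66 | 23.27 − 18.43 = 4.84 (printed 4.85) | 22.82 − 20.74 = 2.08 |
| Left molar | 23.67 − 18.45 = 5.22 (printed 5.21) | 23.71 − 19.09 = 4.62 | 23.01 − 20.49 = 2.52 |
| Right premolar | 11.72 − 6.70 = 5.02 | 8.34 − 6.43 = 1.91 | 8.72 − 7.76 = 0.96 |
| Left premolar | 12.46 − 7.37 = 5.09 | 8.63 − 6.57 = 2.06 | 8.41 − 7.61 = 0.80 |

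All twelve agree within 0.01. One-way ANOVA on the post-treatment summary statistics gives p = 0.734 and 0.890 at the molars (printed .734 and .892), and 0.0033 and <0.001 at the premolars (printed .003 and .000). The means are internally consistent.

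**Step 2: premolar tipping as a fraction of molar tipping**, by side.

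- Conventional: 5.02/5.66 = 0.89 right; 5.09/5.21 = 0.98 left
- Hybrid: 1.91/4.85 = 0.39; 2.06/4.62 = 0.45
- MSE: 0.96/2.08 = 0.46; 0.80/2.52 = 0.32

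Averaged over sides, conventional / Hybrid / MSE is 5.44 / 4.74 / 2.30 at the molar and 5.06 / 1.99 / 0.88 at the premolar.

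**Step 3: arm contrasts at each tooth.** Difference in mean change with a Welch 95% interval, SE = √(s₁²/n₁ + s₂²/n₂). The SAP calls the change data non-parametric, so these intervals are a guide to size and do not replicate its test.

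| Contrast | Right molar | Left molar | Right premolar | Left premolar |
|---|---|---|---|---|
| Conventional − Hybrid | 0.81 (−0.57 to 2.19) | 0.59 (−1.11 to 2.29) | 3.11 (1.82 to 4.40) | 3.03 |
| Conventional − MSE | 3.58 (2.54 to 4.62) | 2.69 (1.06 to 4.32) | 4.06 (2.83 to 5.29) | 4.29 |

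The printed post hoc letters agree with the Hybrid row: conventional and Hybrid are a and a at both molars, a and b at both premolars.

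No left-premolar interval is reliable, because the printed change SDs (5.09, 2.06, .80) repeat the means in all three arms. Substituting the right-side SDs gives 1.74 to 4.32 against Hybrid and 3.06 to 5.52 against MSE. Substituting the post-value SDs gives 0.98 to 5.08 and 2.14 to 6.44.

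**Step 4: a second measure.** Change in distance (outcome Table 1), conventional / Hybrid / MSE, is 5.88 / 7.42 / 8.88 at the molars and 6.68 / 6.08 / 4.43 at the premolars. The order of the arms reverses between teeth.

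**Step 5: narrative against table.** The SAP narrative says the inclination change was significantly higher in MSE than in both other arms, for molars and premolars alike. Outcome Table 2 shows MSE lowest in all four comparisons. For the premolars, the narrative also reports no pre-treatment difference and the highest post-treatment value in the conventional arm, which fits the table.

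**The case against.** The strongest case for the plan is that the molar is the most-tipped measured tooth in every arm (5.44 against 5.06, 4.74 against 1.99, 2.30 against 0.88). If risk follows tipping, it is a defensible common index tooth, and adding premolars is partly a design preference. This stands as a reason to keep the molar. It does not make the molar equally representative across arms.

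A reader might infer that the harm comparison favours the conventional expander. The documents do not support that. The conventional arm also tips the molars most, and clearly more than MSE, so on the same proxy a molar-only reading would still rank it worst. There is no periodontal result to be biased, and nothing in the documents links degrees of tipping to loss of bone or gum. Only possible understatement is left.

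The choice of proxy also matters. On distance, conventional and Hybrid differ at the molars (5.88 against 7.42, different letters) and share a letter at the premolars (6.68 against 6.08), the reverse of the inclination pattern. Distance includes skeletal widening and is not a clean measure of dental load. So the claim that these arms separate at the premolar holds for tipping only. On both measures, however, the arm contrast depends on the tooth read.

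Finally, results exist. Choosing a tooth now because it shows the wider contrast is data-driven, and existing scans cannot supply clinical premolar readings. Both points stand and limit the fix. It is also true that no document claims overall periodontal safety.

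**Conclusion.** The point holds in a limited form. Outcome (a) omits a tooth that, by the trial's own figures, is tipped 89% to 98% as far as the molar in the conventional arm and 32% to 46% as far in the other two. The conventional-minus-Hybrid gap in tipping, averaged over sides, is 5.44 − 4.74 = 0.70 at the molar and 5.06 − 1.99 = 3.07 at the premolar. Against MSE the gaps are 5.44 − 2.30 = 3.14 and 5.06 − 0.88 = 4.18, so the understatement would matter less there.

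The conclusion assumes that periodontal risk rises with tipping at a tooth, that outcome Table 2 rather than the narrative is right about direction, and that Butterfly means conventional. The right-side figures carry it without the doubtful left-premolar SDs. Because this is a secondary outcome and the link to harm is untested, it is a low-cost improvement, not a flaw that invalidates the trial.

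**What to change.** 1. Add radiographic periodontal measures at the first premolars, read from the CBCT volumes already acquired and blind to arm where possible. Report them by arm beside the molar measures and label them post hoc.
2. Do not extend the clinical readings to the premolars retrospectively.
3. If the premolars are not read, confine any periodontal conclusion to the first molars and do not present it as the periodontal safety of the appliance.
4. Reconcile the SAP narrative on inclination change with outcome Table 2, correct the left-premolar change SDs from the source data, and use one name for the conventional arm throughout.

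The cost is reading time and one more set of secondary, post hoc measures. No new scan or visit is needed, provided the existing volumes show the premolar bone adequately. The documents do not state this, though measurements at premolar level are already reported. Items 3 and 4 are text and table corrections.

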# **Evaluation of the Effect of Three Types of Rapid Maxillary Expanders (Conventional, Hybrid and MSE)**

**NCT05446714**

**Date of the document:14/5/2024**

### **Statistical analysis**

Data management and statistical analysis were performed using the Statistical Package for Social Sciences (SPSS) version 20. Data were explored for normality by checking the data distribution and using Kolmogorov-Smirnov and Shapiro-Wilk tests. Comparisons of normally distributed numeric variables between groups was performed by ANOVA test followed by Bonferroni post hoc test whenever a significance difference was detected. Pre and post values was compared by paired t test.

The mean difference was calculated by the formula:(Value after-value before)

Difference data were non-parametric and were compared between groups using Kruskal Wallis test.

All p-values are two-sided. P-values  $\leq 0.05$  were considered significant.

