Right.1 st premolar inclination	Butterfly hyrax	6.70	2.51	11.72 a	3.96	5.02 a	2.18	5.90	.000*
	Hybrid hyrax	6.43	1.56	8.34 b	1.63	1.91 b	.98	1.60	.000*
	MSE	7.76	2.16	8.72 b	2.37	.96 b	.51	0.90	.000*
	P value bet. groups	.191ns		.003*		.000*			
Left.1 st premolar inclination	Butterfly hyrax	7.37	2.39	12.46 a	3.48	5.09 a	5.09	5.80	.003*
	Hybrid hyrax	6.57	1.60	8.63 b	1.51	2.06 b	2.06	2.20	.000*
	MSE	7.61	2.17	8.41 b	2.08	.80 c	.80	0.70	.000*
	P value bet. groups	.355ns		.000*		.000*			

Significance level p≤0.05, \*significant, ns=non-significant

Post hoc test: Within the same comparison, means sharing the same superscript letter are not significantly different

Table (3) Descriptive statistics and comparison between (ANOVA test) and within group (i.e. between pre and post value) (paired t test) regarding arch depth; incisor inclination

GROUP	Pre		Post		Amount of change (post-pre)			P Within group	
	Mean	Std. Dev	Mean	Std. Dev	Mean	Std. Dev	Median		
Arch depth	Butterfly hyrax	26.92	2.87	26.19 a	2.47	-.74 a	.38	-.70	.000*
	Hybrid hyrax	25.93	2.47	25.39 a	2.43	-.53 a	.22	-0.50	.000*
	MSE	24.72	2.25	23.38 b	2.41	-	.60	-1.30	.000*
	P value bet. groups	.064ns		.007*		.000*			
Incisor inclination	Butterfly hyrax	117.31	3.65	114.46	3.37	-	2.00	-2.80	.000*
	Hybrid hyrax	118.45	4.29	114.67	4.30	-3.79 a	1.80	-3.70	.000*
	MSE	120.05	5.32	114.63	5.79	-	1.48	-5.30	.000*
		.243 ns		.992 ns		.001*			
Anterior suture opening	Butterfly hyrax	.09	.27	3.57 b	.47	3.47 b	.34	3.50	.004*
	Hybrid hyrax	.27	.44	3.93 b	.64	3.67 b	.36	3.70	.000*
	MSE	.30	.42	5.99 a	.46	5.69 a	.33	5.70	.002*
	P value bet. groups	.290 ns		.000*		.000*			
Posterior suture opening	Butterfly hyrax	.00	.00	2.14 c	.44	2.14 c	.44	2.20	.000*
	Hybrid hyrax	.00	.00	3.06 b	.37	3.06 b	.37	3.10	.000*
	MSE	.00	.00	5.16 a	.49	5.16 a	.49	5.05	.000*
	P value bet. groups	---		.000*		.000*			

Significance level p≤0.05, \*significant, ns=non-significant

Post hoc test: Within the same comparison, means sharing the same superscript letter are not significantly different

[figure not shown]

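### The SAP checks normality but not equal spread, pools variances that differ between arms, and names no pairwise test for change scores

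*SAP*

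**What the plan says.** The Statistical analysis section of the SAP gives one assumption check, "Data were explored for normality by checking the data distribution and using Kolmogorov-Smirnov and Shapiro-Wilk tests". For normally distributed variables, the comparison between arms was "performed by ANOVA test followed by Bonferroni post hoc test whenever a significance difference was detected". Change scores are treated separately: "Difference data were non-parametric and were compared between groups using Kruskal Wallis test". No post hoc test is attached to that sentence, and no unequal-variance method appears anywhere.

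Outcome Tables 1 to 3 each carry the title "Descriptive statistics and comparison between (ANOVA test) and within group", without setting the change column apart. Both the post and the change columns carry superscript letters, and the footnote says that "means sharing the same superscript letter are not significantly different". Tests are two-sided at 0.05.

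In outcome Table 2, right first premolar inclination change has letters a/b/b for Butterfly, Hybrid and MSE. The narrative paragraph on premolar inclination says: "The mean value of amount of change (difference) recorded in MSE was significantly higher than that recorded in Butterfly hydrax and Hybrid hyrax".

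**The concern.** A pooled SD is an average over all three arms. If one arm is much more variable, the pooled value is too small for contrasts that involve that arm and too large for the contrast between the other two. Whether two arms share a letter then depends partly on the third arm's spread. Readers of a three-arm appliance comparison take their pairwise conclusions from those letters, and premolar tipping is a natural contrast between tooth-borne and bone-borne anchorage.

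A normality check does not detect this. Kruskal-Wallis does not remove it either, because it compares location cleanly only when the distributions have similar shape and spread. For change scores there is a further gap: the letters come from a pairwise test that the SAP does not name.

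**Working it through.** **Inputs.** Means and SDs come from the SAP's outcome tables, in the order Butterfly, Hybrid, MSE. Group sizes 15, 15 and 16 are the totals in the SAP's demographic Tables 2 and 3.

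**Formulas.**
- Pooled variance: MSW = Σ(nᵢ−1)sᵢ²/43. Pooled SE = √[MSW(1/nᵢ+1/nⱼ)] on 43 df, with p multiplied by 3 (Bonferroni).
- Unequal-variance SE = √(sᵢ²/nᵢ+sⱼ²/nⱼ), with Satterthwaite df. Games-Howell refers √2·|t| to the studentized range for three groups. Welch's F is used for the overall test.

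**1. Right premolar inclination, post** (means 11.72, 8.34, 8.72; SDs 3.96, 1.63, 2.37; variance ratio 3.96²/1.63² = 5.9; Bartlett p = .005).
- MSW = (14×3.96² + 14×1.63² + 15×2.37²)/43 = 7.93, and the between-group mean square is 51.80. F = 6.53, p = .0033, which reproduces the SAP's .003.
- Welch: p = .020.
- Butterfly−MSE = 3.00. Pooled SE 1.012, t = 2.96, p = .0049, adjusted .015. Unequal-variance SE 1.182, t = 2.54, df 22.6, Games-Howell .047.
- Games-Howell for the other pairs: Butterfly-Hybrid .017, Hybrid-MSE .86. The letters a/b/b stand.

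**2. Left premolar inclination, post** (12.46, 8.63, 8.41; SDs 3.48, 1.51, 2.08; ratio 5.3; Bartlett p = .008).
- ANOVA F = 12.72, p = .00005. Welch p = .0016.
- Games-Howell: .003, .002 and .94. The letters a/b/b stand.

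**3. Nasal floor at the premolar, post** (37.04, 38.63, 39.73; SDs 1.17, 1.77, 2.27; ratio 2.27²/1.17² = 3.8).
- ANOVA F = 8.65, p = .0007, which reproduces the SAP's .001.
- Butterfly-Hybrid, difference 1.59: pooled SE 0.660, t = 2.41, adjusted .061. Unequal-variance SE 0.548, t = 2.90, df 24.3, Games-Howell .021.
- Hybrid-MSE, difference 1.10: pooled .29, Games-Howell .30.
- The printed letters are c/b/a, with all three arms different. Neither method gives that.

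**4. Right premolar inclination, change** (5.02, 1.91, 0.96; SDs 2.18, 0.98, 0.51; ratio 2.18²/0.51² = 18.3).
- MSW = (14×2.18² + 14×0.98² + 15×0.51²)/43 = 1.95, pooled SD 1.40.
- Hybrid−MSE = 0.95. Pooled SE 0.502, t = 1.89, p = .065, adjusted .196. Both Butterfly contrasts are below .001. This reproduces a/b/b.
- Unequal-variance SE = √(0.98²/15 + 0.51²/16) = 0.283, t = 3.35, df 20.8. Games-Howell .008, simultaneous 95% interval 0.24 to 1.66.
- Rank tests need raw data, so they were simulated on data forced to the printed means and SDs under three assumed shapes. Dunn-Bonferroni for Hybrid-MSE had median p of .075 to .092 and was significant in 7% to 22% of data sets. Pairwise Mann-Whitney had median p of .002 to .004.

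**5. Which tests produced the change columns?** Allowing for rounding of the inputs, ANOVA would give:

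| Change score | Printed p | ANOVA range |
|---|---|---|
| Molar rotation, right | .503 | .549–.611 |
| Premolar distance | .005 | .0037–.0041 |
| Molar inclination, left | .003 | .0010–.0012 |

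These overall tests were not ANOVA, which fits the Kruskal-Wallis sentence. The letters point the other way. Pooled Bonferroni gives the printed patterns for right premolar inclination, molar distance (adjacent pairs .033 and .042), premolar distance (Hybrid-MSE .048) and nasal floor at the premolar (Butterfly-Hybrid .007). Simulated Dunn-Bonferroni never gave the molar distance or nasal floor pattern.

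**6. Table against narrative.** Quote "The mean value of amount of change (difference) recorded in MSE was significantly higher than that recorded in Butterfly hydrax and Hybrid hyrax" is the SAP's wording for premolar inclination. In Table 2 the right-side MSE change, 0.96, is the lowest of the three, and it shares letter b with Hybrid.

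**The case against.** The strongest reply is that the most striking row, right premolar inclination change, is a change score. The SAP text assigns change scores to Kruskal-Wallis, not to ANOVA, and step 5 suggests the overall test was indeed not ANOVA. That stands. Pooling in the change columns is inferred from the letters and the table titles; it is not something the SAP text prescribes. What the documents do support is that the post hoc test is unnamed and that the letters checked look like pooled Bonferroni laid over a rank test.

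It also stands that in both premolar inclination post rows every significance call survives Welch and Games-Howell. The margin for Butterfly-MSE on the right side is thin: Welch t with Bonferroni gives .056.

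Stronger readings that a reader might infer are not supported:
- *That Hybrid and MSE are reported as equal.* A shared letter means not significantly different, and the narrative says that they differ.
- *That the raw data must give a/b/c.* Games-Howell and Mann-Whitney separate Hybrid from MSE; Dunn-Bonferroni usually does not.
- *That 18-fold is the largest variance ratio.* Left premolar rotation change gives (2.50/0.32)² = 61, though no conclusion changes there.
- *That molar distance change is a further example.* Hybrid-MSE moves from .042 to .057, but the SDs are 1.39, 1.77 and 1.58 (ratio 1.6), so unequal spread is not the cause.

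**Conclusion.** The point holds in a limited form. The SAP describes no check of equal variance and no method that allows for unequal variance, although spread differs clearly between arms. In the post values, where ANOVA is prescribed, the evidence on premolar inclination is overstated (.003 against .020; .00005 against .0016) without reversing a call. One pairwise comparison, nasal floor at the premolar, Butterfly against Hybrid, crosses .05 in the other direction (.061 to .021). The letters printed in that row match neither method.

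For change scores the pairwise method is unspecified, the table titles conflict with the text, and at least one letter depends on the method chosen. The narrative on premolar inclination contradicts Table 2 in direction, and on the right side in significance as well.

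This rests on the printed means and SDs being correct, on 15, 15 and 16 patients contributing to every outcome, and on approximate normality for the mean-based tests. Left premolar inclination change was not used, because its SD column repeats the means. Most of the trial's conclusions are not affected.

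**What to change.** 1. In the Statistical analysis section, replace ANOVA with Bonferroni by Welch ANOVA with Games-Howell for comparisons of means between arms.
2. Amend the Kruskal-Wallis sentence so that change scores use either that same method or Kruskal-Wallis with a named, multiplicity-adjusted post hoc test. Changing only the ANOVA sentence would leave the change scores where they are.
3. Rerun on the raw data and reissue all letters, without presuming the pattern for right premolar inclination change. Check the nasal floor premolar post letters in particular.
4. Make the table titles name the test used in each column, and reconcile the premolar inclination narrative with Table 2.

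The SAP already contains results, so the revision should be recorded as made after the data were seen. The cost is two SAP sentences, one rerun in SPSS, and slightly lower power where variances are equal.
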